#### **14.2. Planned Statistical Analysis**

##### **Fetal Heart Rate analysis**

Fetal heart rate tracings will be analyzed in 1.0 second epochs.

Endpoint 1.1 – FHR interpretability.

The fraction of epochs that report an interpretable value over the recording period will be determined for ECG and Doppler tracings for each subject as a modified sensitivity. Values for all subjects will be averaged to yield a mean modified sensitivity for each monitoring modality. We anticipate finding the fetal heart rate interpretability rate will equal or exceed the interpretability rate for Doppler.

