#### **Maternal Heart Rate monitoring**

Maternal heart rate data are sometimes confused with fetal heart rate data, and it is clinically useful to independently measure the maternal heart rate. If different rates are obtained, it is clear that the fetal heart rate reported by the monitor does indeed come from the fetus. Legacy recording of the maternal heart rate occurs through use of a pulse oximeter placed on the maternal finger.

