#### **Area uEMG sensors**

In our research, we discovered that ECG-type pads are poorly suited to record uterine signals because of major differences of physiology between the organs [7]. In brief, heart signals travel parallel with the skin, while uterine signals arise from below. This phenomenon results in circular pads detecting only very small signals that are difficult to separate from background noise. To more efficiently measure the rising uterine signals, we developed a directional sensor, (which we call “area sensor”). These were evaluated at URMC under RSRB#59426 in 2016-2017. These uEMG sensors are made from the same material as standard ECG pads, but differ only in shape – an open hexagon, measuring 6 cm x 6 cm, (i.e. the hexagon surrounds an open “area”). The unique shape confers directionality to the sensor, efficiently sensing signals that arise from below. This gives our sensors the ability for typical signal detection of 1500  $\mu$ V, which is 5 times greater voltage than the largest voltage reported using pad-type sensors. Furthermore, our sensors provide for, the first time, spatial resolution to identify local uterine contractile activity.

Not surprisingly, both the fetal and maternal ECG is also observable using our area sensors.

Further study is required to convert and display these signals into clinically useful fetal and maternal heart rates.

Though this study, we anticipate that by measuring the extent of synchronization of several regions on the uterus, we will be able to determine which contractions represent true labor, and which represent false labor. First generation EMG analysis measures the relative power of the signals coming from the uterus. Our method analyzes the timing of events from the many sensors/regions that sample a large surface of the uterus, a procedure called “event analysis”. Furthermore, we hypothesize that a transition from unsynchronized regional contractions to fully synchronized contractions will represent the onset of true labor.

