#### Endpoint 1.2 – FHR accuracy.

Bland-Altman difference plots (using epochs) of ECG v Doppler will be created for each subject. RMS error will be calculated, where  $RMS = [\text{average}(\Delta^2)]^{0.5}$ . This calculation yields an RMS for each subject; a mean RMS error will then be calculated for ECG against Doppler as gold standard. We anticipate finding the fetal heart rate accuracy will equal or exceed the accuracy of Doppler.

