### **Maternal Heart Rate analysis**

Maternal heart rate will be calculated from the maternal ECG as recorded by the PreTel Monitor. These maternal heart rates will be compared with the corresponding maternal heart rates obtained from the gold standard pulse oximeter. Heart rate data will be analyzed in 0.25 second epochs, and the epochs will be analyzed for interpretability and accuracy in an identical manner as the fetal heart rate endpoints 1.1 and 1.2.

The sensitivity for monitoring contractions in subjects without an IUPC placed, modified S, will be analyzed as described for run-in subjects described in Objective 2, endpoint 2.4a. Objective 2. To determine the efficacy of PreTel's fetal monitor against the external standard of care and internal gold standard of fetal monitoring.

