### **Fetal Heart Rate analysis**

Fetal heart rate tracings will be analyzed in 1 second epochs.

Endpoint 2.1 – FHR interpretability. “PPA” is positive percent agreement for ECG or Doppler vs gold standard (GS). 2x2 tables for interpretable and uninterpretable data using ECG or Doppler versus FSE will be created. The presence of a “valid” FHR using ECG or Doppler will be tested against a valid FSE (as GS) in each epoch. PPA = percent of epochs with “valid GS reading” that also has a valid reading by ECG or Doppler.

Endpoint 2.2 – FHR accuracy. Bland-Altman difference plots (using epoch values) of test vs gold standard will be created for each subject (hence two plots for each subject). RMS error will be calculated from data for each device. RMS = [average(delta^2)]^0.5. This yields an RMS for each subject for each device, then mean RMS errors will be reported for ECG and Doppler.

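### Endpoint 1.1 does not exclude epochs in which the reported fetal rate is the mother's, and it compares ECG with Doppler through two means without an interval

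*Combined protocol and SAP*

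**What the plan says.** **Endpoint 1.1** (Section 14.2, Fetal Heart Rate analysis) works in 1-second epochs. For each subject and device it takes "The fraction of epochs that report an interpretable value over the recording period". It then states: "Values for all subjects will be averaged to yield a mean modified sensitivity for each monitoring modality". The expectation follows: "We anticipate finding the fetal heart rate interpretability rate will equal or exceed the interpretability rate for Doppler". No SD, interval, test or margin is given, and *interpretable* is not defined.

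**Endpoint 1.2** measures accuracy by per-subject Bland-Altman plots and RMS error: "a mean RMS error will then be calculated for ECG against Doppler as gold standard".

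**Endpoint 2.1** takes epochs with a valid scalp-electrode (FSE) reading and counts the percentage "that also has a valid reading by ECG or Doppler". *Valid* is also undefined. **Endpoint 2.2** then gives Bland-Altman plots and RMS errors of ECG and of Doppler against the gold standard. Neither accuracy endpoint has an acceptance limit.

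**Maternal rate.** Section 1.2 warns: "Maternal heart rate data are sometimes confused with fetal heart rate data". It adds that differing maternal and fetal rates confirm that the displayed fetal rate is fetal. On the study sensors, the same section says "both the fetal and maternal ECG is also observable using our area sensors". The only analysis planned for the maternal rate in Section 14.2 is a device check: "These maternal heart rates will be compared with the corresponding maternal heart rates obtained from the gold standard pulse oximeter".

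**The concern.** The protocol names a specific way in which a fetal monitor can show a plausible but wrong number, describes the check that exposes it, and collects a signal for that check. It does not apply the check to the fetal endpoints. The risk concerns the test device directly, because its sensors pick up both ECGs.

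An interpretability fraction without such a rule can rise because a device reports more wrong values. The epochs that matter most are those in which ECG reports and Doppler does not. They raise ECG interpretability relative to Doppler, and endpoint 1.2 cannot examine them because there is no Doppler value to subtract.

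Separately, the anticipated result would be read from two point estimates with no statement of uncertainty. Section 2.1 says the study seeks to validate how reliably the monitor determines the fetal heart rate, so a reader may give that comparison more weight than it can carry.

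**Working it through.** **Stated figures.** The plan gives no sample size or precision for fetal heart rate interpretability. The 23 in Section 14.1 belongs to the contraction aim. It reproduces as a one-sample proportion, 0.75 against 0.50, one-sided alpha 0.05, power 0.80 (reading the printed beta of 0.8 as power): (1.645×0.5 + 0.842×√(0.75×0.25))² / 0.25² = 22.5, rounded up to 23. The plan does not say which formula was used. I use 23 and the recruitment ceiling of 50 only as plausible numbers of women.

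**1. How much maternal signal would close a gap?** Section 1.2 says legacy non-invasive monitoring is ineffective 15% of the time on average. As an illustration, take Doppler interpretability as 1 − 0.15 = 0.85. If ECG gives true fetal readings in a share f of epochs, the maternal share needed to reach 0.85 is 0.85 − f.

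| True fetal share f | Maternal share needed | As share of ECG-reported epochs |
|---|---|---|
| 0.80 | 0.05 | 0.05/0.85 = 5.9% |
| 0.75 | 0.10 | 0.10/0.85 = 11.8% |
| 0.70 | 0.15 | 0.15/0.85 = 17.6% |

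**2. Would the accuracy endpoints show it?** Assume a maternal-fetal gap of 60 bpm and an error of 3 bpm elsewhere.

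- Where a correct reference reading exists and 10% of compared epochs are maternal: RMS = √(0.1×60² + 0.9×3²) = √368.1 = 19.2 bpm. That is plainly visible against 3 bpm.
- Where the maternal epochs all fall in Doppler loss: endpoint 1.2 has no pair to difference. Its RMS stays at 3 bpm, while endpoint 1.1 still credits those epochs if they count as interpretable.
- Where Doppler itself has locked on to the mother: endpoint 1.2 charges the error to ECG. If both devices lock on, they appear to agree.

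Endpoint 2.2 avoids the last two problems, but only in women with FSE. Section 1.2 says invasive monitoring requires ruptured membranes, Section 5.1 requires a clinical indication, and Section 3.2 requires less than 3 cm dilation. The number of such women is not stated and may be small.

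**3. Reading the comparison without an interval.** Let the true ECG deficit be d SDs of the within-subject difference. By the normal approximation, P(mean ECG ≥ mean Doppler) = Φ(−d√n).

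| d (assumed) | n = 23 | n = 50 |
|---|---|---|
| 0 | 50% | 50% |
| 0.1 | 31.6% | 24.0% |
| 0.2 | 16.9% | 7.9% |
| 0.3 | 7.5% | 1.7% |

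**4. What an interval would give.** The documents give no SD for the difference, so I take 0.05, 0.10 and 0.20. The 95% half-width is t × SD/√n. At n=23 it is 2.2, 4.3 or 8.6 percentage points; at n=50 it is 1.4, 2.8 or 5.7 points.

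**The case against.** The plan separates two questions: whether there is a reading (1.1, 2.1) and whether it is right (1.2, 2.2). That is a legitimate structure, and step 2 shows that the accuracy endpoints would reveal substantial maternal substitution wherever a correct reference value exists. This is a feasibility pilot, so formal inference is not required.

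Much of this stands, and it rules out several stronger readings that a reader might infer:

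- *That the plan counts any displayed rate as interpretable, maternal or not.* It does not say so. The terms are undefined, so maternal readings are not excluded rather than expressly counted.
- *That 2.1 leaves disagreement with FSE unexamined.* Every epoch that 2.1 scores as agreement has both values, and 2.2 examines them. Building a tolerance into 2.1 is a design preference.
- *That doing at least as well as Doppler is a success criterion.* It is an anticipation, attached to 1.1 and not to 2.1, with no decision rule.
- *That averaging the devices separately distorts the comparison.* When every woman contributes both devices, the difference of the two means equals the mean paired difference. The problem is the missing interval.

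A coincidence rule also has limits. Maternal and fetal rates can truly be close, so a rule may remove genuine fetal readings. The maternal ECG comes from the device under test and is not independent of it. The oximeter is independent, but it is not in Section 5's required concurrent monitoring or Section 2.1's case report form list.

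What the objection leaves standing is the gap in 1.2 during Doppler loss, the restriction of 2.2 to women with FSE, and the lack of any interval in 1.1.

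**Conclusion.** The point holds in a limited form. Endpoint 1.1 lacks a rule for epochs in which the reported fetal rate is maternal, and the accuracy endpoints cover that gap only in part. Its comparison with Doppler also lacks a measure of uncertainty.

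On size: with Doppler taken as 0.85, a maternal share of 5 to 15% of epochs would offset a true ECG shortfall of 5 to 15 points. Without an interval, a truly worse ECG would look equal or better with probability of about 32%, 17% or 8% at n=23 for deficits of 0.1, 0.2 or 0.3 SD. The maternal share, the 60 bpm gap, the 3 bpm error, the SDs and the deficits are all assumptions; the documents give none of them. Nothing in the documents shows that maternal substitution occurs often with this device.

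The change is worth making. The gap does not invalidate the study.

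**What to change.** 1. Before analysis, define *interpretable* and *valid*, and fix a maternal-coincidence rule: the tolerance, the minimum duration, and the maternal source. Prefer the pulse oximeter where it is recorded, and say which source was used for each subject. State how the 0.25-second maternal epochs map to the 1-second fetal epochs.
2. Apply the rule identically to ECG and Doppler. Report 1.1 with and without flagged epochs, and show separately the ECG epochs that fall in Doppler loss.
3. Report the per-subject ECG-minus-Doppler difference in interpretability with a 95% CI. If non-inferiority is meant, state a margin.
4. Optionally, add a secondary 2.1 agreement percentage that requires the value to lie within a prespecified tolerance of FSE, alongside the existing one and 2.2.

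The cost is some extra analysis on planned recordings, with no added patients or procedures. An independent maternal check is possible only where oximetry is kept. The flagged version may discard some true fetal epochs when the two rates are close, which is why both versions are reported.

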#### Endpoint 1.2 – FHR accuracy.

Bland-Altman difference plots (using epochs) of ECG v Doppler will be created for each subject. RMS error will be calculated, where  $RMS = [\text{average}(\Delta^2)]^{0.5}$ . This calculation yields an RMS for each subject; a mean RMS error will then be calculated for ECG against Doppler as gold standard. We anticipate finding the fetal heart rate accuracy will equal or exceed the accuracy of Doppler.

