#### **Legacy fetal monitoring - Invasive fetal monitoring.**

Because ongoing assessment of the fetus is critically important, invasive monitoring is often performed when non-invasive legacy methods fail. Here, a fetal scalp electrode (FSE) is used to measure the fetal heart rate, and an intrauterine pressure catheter (IUPC) is used to measure uterine contractions.

For the FSE, a silver wire is attached to the fetal scalp. This provides direct electrical contact with the fetus and allows recording of a reliable ECG signal for heart rate determination. The IUPC is a tube that is inserted through the vagina and cervix, and into the uterine cavity. The IUPC reports the pressure generated inside the uterus, which is a direct measure of the contraction forces produced. The use of these internal direct measurements is considered the gold standard for fetal monitoring.

Use of invasive monitoring requires that the amniotic membranes be ruptured (either naturally or intentionally). Thus, there are potential complications that arise in the setting of IUPC/FSE monitoring, most commonly maternal fever [4], which is suggestive of intrauterine infection.

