For both the preterm or term subjects who present to triage, there is the possibility that they may not ultimately progress in labor. These subjects are also eligible for an EMG study session for 60 minutes while their labor status is being evaluated. If they are deemed to not be in labor (i.e. no cervical change) and are discharged (or admitted for extended monitoring, as may occur in the preterm setting or at term for “therapeutic rest”), they will not be excluded from analysis, and they will be allowed to participate in another session either when they begin laboring (i.e. if admitted) or if they are discharged and then return to Triage for another labor evaluation. Recordings may be stopped and restarted multiple times for a single subject if needed.

During the 60+ minutes of EMG pad placement, subjects must also have standard tocometry monitoring and fetal heart rate monitoring. The standard monitoring can consist of either external tocodynamometry (Toco) or an intra-uterine pressure catheter (IUPC) and either external Doppler monitoring of the fetal heart rate or a fetal scalp electrode (FSE). Which type of monitoring is used will be at the discretion of her regular obstetric care team and will not be altered by participating in the study (i.e., the study will not require the patient to have internal monitoring IUPC/FSE). Participation during the 60 minutes of recording does however require some form of continuous monitoring, and therefore subjects desiring intermittent fetal heart rate auscultation or intermittent palpation for contractions, will not be eligible for participation unless they are willing to have standard monitoring for the duration of the study period. Clinical decisions will only be made based on standard uterine and fetal monitoring and examinations.

Uterine EMG recordings, along with the fetal monitoring paper record, will be sent to PreTel. Assessment of the recordings for uterine contractility and fetal heart rate will then be performed by those investigators trained in the analysis ([name]). The EMG data will be compared to the tocometry data to determine correlation or “R” value.

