### **14.3. Data and Safety Monitoring**

This study entails no more than minimal risk to the patient and fetus. As such, the study does not need a Data and Safety Monitoring committee. Oversight and monitoring of the conduct of the progress of the study will be the responsibility of the local investigators. Concern for the safety and wellbeing of the patients will be reported to the local investigators who will in turn contact the study Sponsor. Data validity and integrity will be handled by [name] following transfer of the de-identified uEMG data.

Endpoint 2.4a – Uterine contraction sensitivity and accuracy. A table of individual contractions identified by EMG, Toco and IUPC will be generated. Contractions detected by EMG or Toco within +/- 30 seconds of IUPC will be defined as True Positive (TP) detections. False Negative (FN) detections are defined as those contractions not detected by EMG or Toco, but detected by IUPC.

Sensitivity, S, for both EMG and Toco, will be calculated as

$$S(\text{EMG or Toco}) = \frac{\text{TP}}{\text{TP} + \text{FN}}$$

For training purposes, the data on laboring patients using non-invasive methods (i.e., not using IUPC) will be analyzed using a modified calculation for S where Toco positive will be used as a proxy gold standard.

$$\text{Modified S (EMG)} = \frac{\text{EMG positive}}{\text{Toco positive} + \text{apparent FN}}$$

Endpoint 2.4b – Contraction timing accuracy.

$\Delta t$  is a measure of the capability of each method to detect the timing of each contraction compared to gold standard.  $\Delta t$  is defined as the time the contraction peak is detected by EMG or Toco minus the time the peak is detected by IUPC in the corresponding contraction.

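### Endpoint 1.2 treats Doppler as the gold standard but measures only ECG–Doppler agreement, so it cannot show that ECG is more accurate than Doppler or which device is in error

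*Combined protocol and SAP*

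**What the plan says.** Under Endpoint 1.2 in Section 14.2, "Bland-Altman difference plots (using epochs) of ECG v Doppler will be created for each subject". One RMS of the differences is computed per subject, and the mean over subjects is reported as an error for "ECG against Doppler as gold standard. We anticipate finding the fetal heart rate accuracy will equal or exceed the accuracy of Doppler". No RMS is planned for Doppler itself, and no third tracing enters the endpoint.

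Elsewhere the protocol gives Doppler a different standing. The background on invasive monitoring (Section 1.2) says of the scalp electrode (FSE) and pressure catheter: "The use of these internal direct measurements is considered the gold standard for fetal monitoring". In Endpoint 2.1 a valid ECG or Doppler reading "will be tested against a valid FSE (as GS) in each epoch", so Doppler is there a device under test. Endpoint 2.2 compares both devices with that reference ("hence two plots for each subject"): "This yields an RMS for each subject for each device, then mean RMS errors will be reported for ECG and Doppler". For contractions without a catheter, Endpoint 2.4a has a more careful description of the external method, "where Toco positive will be used as a proxy gold standard".

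**The concern.** The statistic and the sentence after it do not fit together. A difference between two devices shows how closely they agree. It does not show how close either is to the true fetal heart rate, and it cannot rank them. Followed as written, the report would present agreement under the title of accuracy and would count every epoch of Doppler error against the ECG.

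A large RMS would not say which device failed. A small one would not show that either device is right, because errors made by both at once look like agreement. Section 1.2 itself describes a candidate mechanism, confusion of maternal with fetal heart rate. The maternal analysis in Section 14.2 uses a pulse-oximeter rate that could flag such epochs, but the plan does not use it to check the fetal rate.

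**Working it through.** The plan states no error SD, margin or expected RMS for fetal heart rate, so there is no figure to reproduce. (The sample size of 23 in Section 14.1 concerns uEMG against tocodynamometry.) The check applies the plan's own formula, RMS = [average(Δ²)]^0.5. All bpm values and FSE shares below are assumptions.

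**1. Doppler taken as truth.** RMS(Doppler − Doppler) = 0, and RMS(ECG − Doppler) ≥ 0. ECG can never have the smaller error. It ties only if every epoch is identical.

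**2. Doppler not taken as truth.** Write ECG = T + e and Doppler = T + d, with T the true rate. Then

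RMS² = (bias_E − bias_D)² + var(e) + var(d) − 2cov(e,d).

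Swapping the devices changes nothing. With zero bias, error SDs of 2 and 6 bpm and error correlation r, RMS² = 4 + 36 − 2·r·2·6 = 40 − 24r:

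- r = 0: √40 = 6.32
- r = 0.5: √28 = 5.29
- r = 0.9: √18.4 = 4.29

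The values are the same whether ECG has SD 2 and Doppler 6, or the reverse.

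**3. What a small value does show.** On shared epochs the reverse triangle inequality gives |RMS_E − RMS_D| ≤ RMS(ECG − Doppler) for each subject, and hence for the means. A mean RMS difference of 2, 5 or 10 bpm limits the gap between the devices' mean RMS errors to 2, 5 or 10 bpm, in either direction. In step 2 the true gap is 6 − 2 = 4, inside the bound each time.

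**4. Shared error.** Suppose both devices track the maternal rate in the same share p of epochs, G bpm from the fetal rate, with independent noise of SD 1 bpm each. The RMS difference is √(1 + 1) = 1.41 whatever p and G are. Each device's true RMS error is √(pG² + 1):

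- p = 0.02, G = 40: √33 = 5.74
- p = 0.05, G = 60: √181 = 13.45
- p = 0.10, G = 60: √361 = 19.0

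**5. Subjects available for Endpoint 2.2.** That endpoint needs ECG, Doppler and FSE together. If a share f of N subjects has all three, the expected number is N·f and the chance of none is (1 − f)^N. N is 23 (the calculated size) or 50 (the recruitment ceiling).

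| f | Expected of 23 | Chance of none | Expected of 50 | Chance of none |
|---|---|---|---|---|
| 2% | 0.5 | 63% | 1 | 36% |
| 5% | 1.2 | 31% | 2.5 | 8% |
| 10% | 2.3 | 9% | 5 | 0.5% |
| 20% | 4.6 | 0.6% | 10 | under 0.1% |

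The 95% CI half-width for a mean paired difference, in SDs of that difference, is t(0.975, n − 1)/√n: 8.98, 2.48, 1.24, 0.72 and 0.43 for n = 2, 3, 5, 10 and 23.

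**The case against.** The strongest reply is that the plan already contains the right comparison in Endpoint 2.2, and that the sentence in Endpoint 1.2 is an expectation in a pilot study with no test, margin or decision rule attached. Both points are true and limit the consequences. They do not repair Endpoint 1.2, whose title and error label invite the accuracy reading. Endpoint 2.2 as written has no interval, no common-epoch rule and no stated number of subjects.

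The FSE group may also be larger than feared. Section 3.2 admits women with indications for internal monitoring, artificial rupture of membranes, or premature rupture with augmentation, and Section 5 allows repeat sessions. This stands as a caution against calling the group empty. But FSE is placed only on clinical indication (Section 5.1), needs ruptured membranes (Section 1.2), and eligibility is below 3 cm dilation (Section 3.2). Section 5 asks for "either external Doppler monitoring of the fetal heart rate or a fetal scalp electrode (FSE"), which permits both but requires only one.

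Three further points stand in part. The shared-error example assumes both devices fail in the same epochs, which the documents do not claim. The bound in step 3 gives Endpoint 1.2 some information on similar accuracy, though none on direction. And calling Doppler a proxy would not by itself let the endpoint rank the devices; the limit is the missing third reference.

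**Conclusion.** The concern holds and should be fixed. That Endpoint 1.2 cannot rank the devices or assign error follows from the algebra and needs no assumed value. The inconsistent standing of Doppler is plain from the text. The size of a possible misreading depends on assumptions: in the shared-error case, an RMS difference of 1.4 bpm would accompany true errors of 5.7 to 19.0 bpm for 2–10% of epochs and gaps of 40–60 bpm.

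Whether ECG exceeds Doppler can be examined only in subjects with simultaneous ECG, Doppler and FSE tracings. The documents do not say how many there will be.

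**What to change.** **Endpoint 1.2.** Rename it ECG–Doppler agreement and call Doppler a proxy reference, in line with the treatment of Toco in Endpoint 2.4a. Report bias, 95% limits of agreement and RMS difference, and state whether the limits are per subject, as the planned plots are, or pooled. Delete the sentence on equalling or exceeding Doppler's accuracy.

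**Endpoint 2.2.** Move that expectation here. In subjects with all three tracings, report the paired per-subject difference RMS(ECG − FSE) minus RMS(Doppler − FSE) on common epochs, with a 95% CI and the number of subjects, labelled descriptive. If there are no such subjects, or too few for an interval, state that relative accuracy was not assessed.

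**Cost.** SAP wording, a common-epoch rule, standard Bland–Altman summaries and one confidence interval. On common subjects and epochs the mean paired difference equals the difference of the two means already planned. No new data are needed where Doppler and FSE happen to be recorded together, but no procedure requires both. The price is that Endpoint 1.2 then supports agreement only, and the relative-accuracy group may be very small or empty. The relabelling stops shared error being read as accuracy; it does not detect it.
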